**(Mon to Fri 09.00 – 17.00)**

## 6. STATISTICS AND DATA ANALYSIS

Parametric tests will be performed on the patients' clinical data to make sure that the sample is homogeneous and consistent with the other literature series reporting similar diseases.

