The patient will be anesthetized and be placed on the surgical table. WHO checklist will be performed and the operating procedure will be carried out as standard NHS practice. During surgery, the operating surgeon will be using standard NHS neurosurgical equipment such as an endoscope and/or a microscope. From the surgeon's perspective, this equipment is operated in exactly the same way as with any other procedure. The only technical modification would be that either the microscope or the endoscope in use will be connected to the system of camera and filters for multispectral/hyperspectral analysis. Use of this imaging acquisition technique will not change standard operative practice, nor will it interfere with the principles of neurological surgery. During each surgical intervention, tissue-specific spectral data will be collected at specific stages - mostly once the brain surface is exposed and at the end of the resection on the surgical cavity. It is important that there is a method of comparing the spectral data generated by multispectral imaging to the nature of the tissue being dissected. In order to do this, we plan to visually record the operation in order to sync visual data with the spectral data obtained at the same moment in time. The video recording will not be patient identifiable and will be viewed only by members of the research team working on this project (see below). The use of video recording equipment will be included in the patient information sheet given to all patients prior to gaining consent.

Pseudo-anonymized clinical data will also be collected on College computers to be matched with intra-operative data. Specifically, the researchers will collect:

- clinical data such as diagnosis, age, sex, clinical status, medical background – this data collection will be performed to ensure that our population is homogeneous according to common statistical parametric tests; moreover, some clinical information (such as the neurological baseline of the patient) will be crucial in order to quantify exactly the degree of reliability of the multispectral signal for eloquent areas detection;
- radiological and histological data – this data collection will be performed for the purpose of the correlation between the multispectral signal and the radiological and/or histological findings;

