#### **4.3. INCLUSION CRITERIA:**

- Above the age of 18, no upper age limit
- Sex: male or female
- Candidates for surgery due to a confirmed clinical and radiological diagnosis of cranial intrinsic or extrinsic tumour – any histological diagnosis confirming neuro-oncological disease, including primary and secondary disease
- Agreed to take part to the present research protocol and signed proper informed consent form

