## 6.1. FIRST AIM

*Detect structural differences between brain tumour tissue and surrounding brain.*

The Regions Of Interest (ROI) for multispectral/hyperspectral acquisition will be delineated on both peri-operative images (MRI scan) and intra-operative images as extrapolated from the intra-operative videos. We will focus our analysis on three main regions:

- normal brain tissue - brain tissue not infiltrated by tumour or edema, nor grossly pathological on pre-operative images or intra-operative images;
- suspected infiltrated brain tissue – tissue surrounding the tumour where there is strong radiological and clinical suspicion of infiltrative disease or edema;
- tumour tissue – margins and core of the tumour on pre-operative images and intra-operative findings.

The signal in one region of the tumour will be compared to a neighbouring 'healthy' region. The signal itself will come from a processed set of images of the brain, where we will fit the data using one of our established models to extract an indication of tissue oxygenation (as a %) on a per-pixel basis.

The comparison between the set of readings obtained from normal brain will be performed using Principal Component Analysis (PCA) and Linear Discriminant Analysis (LDA) or more advanced techniques including, for example, machine learning. Statistics will be collected on accuracy, sensitivity, specificity, ROC analysis.

We will also need to take pictures and/or videos of the surgical field in order to correlate the expected anatomical location of the tumour and infiltrated areas with the intra-operative finding. The surgical field is limited to the area under the microscope or endoscope

magnification, therefore no identifiable pictures or videos will be taken at any point during the study.

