## 6.2. SECOND AIM

*Detect differences between eloquent/functional and non-eloquent/non-functional brain areas.*

The Regions Of Interest (ROI) for multispectral/hyperspectral acquisition will be delineated on both peri-operative images (MRI scan) and intra-operative images as extrapolated from the intra-operative videos. For the purpose of this subsection, we will focus our analysis on the comparison between a supposed eloquent area and its surrounding brain tissue. In order to achieve this, we will consider to perform multispectral/hyperspectral acquisition on patients undergoing surgery with neurophysiology monitoring - Motor Evoked Potentials (MEP), SomatoSensory Evoked Potentials (SSEP), Visual Evoked Potentials (VEP), Auditory Evoked Potentials (AEP) - , and/or in patients undergoing awake surgery.

The presence of eloquent brain tissue will be confirmed both anatomically by identifying it on peri-operative and intra-operative assessment, and through neuromonitoring stimulation and/or the execution of a single task during awake surgery, as standard clinical practice in surgery for brain tumours in eloquent areas. From this point of view, clinical correlation with the patient's pre-operative neurological status is crucial in order to consider potential variations in the strength of the intra-operative signal and activation pattern of the analysed eloquent areas – example: a patient with a pre-operative limb weakness is expected to show a different level of activation and therefore might show a different spectroscopic signal compared to a patient with normal motor power. We will also need to take pictures and/or videos of the surgery in order to correlate the expected anatomical location of an eloquent area with the intra-operative finding. The surgical field is limited to the area under the microscope or endoscope magnification, therefore no identifiable pictures or videos will be taken at any point during the study.

Same tests as section 6.1 will be run to statistically validate the data.

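### Parametric tests cannot make sure the sample is homogeneous, and the intended links of the signal to histology and pre-operative deficit have no stated method

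*Combined protocol and SAP*

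**What the plan says.** Section 6 opens its statistical plan with: "Parametric tests will be performed on the patients' clinical data to make sure that the sample is homogeneous and consistent with the other literature series". Section 4.1 gives the same reason for collecting diagnosis, age, sex, clinical status and medical background: "this data collection will be performed to ensure that our population is homogeneous according to common statistical parametric tests".

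Section 4.3 admits patients with "cranial intrinsic or extrinsic tumour – any histological diagnosis confirming neuro-oncological disease, including primary and secondary disease".

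For Aim 1, Section 6.1 states: "The signal in one region of the tumour will be compared to a neighbouring" healthy region. It names PCA with LDA, or more advanced methods such as machine learning, and adds: "Statistics will be collected on accuracy, sensitivity, specificity, ROC analysis". For Aim 2, Section 6.2 plans a "comparison between a supposed eloquent area and its surrounding brain tissue" and closes by referring back to the tests of 6.1.

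Two further intentions are stated. Section 4.1 collects radiological and histological data so that the multispectral signal can be correlated with those findings. It also says that clinical information "such as the neurological baseline of the patient) will be crucial in order to quantify exactly the degree of reliability" of the signal for detecting eloquent areas. Section 6.2 likewise calls correlation with pre-operative neurological status crucial. Its example is limb weakness, which it expects to alter activation and perhaps the spectroscopic signal.

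**The concern.** There are two separate issues.

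The first is the inference. A significance test can give evidence of a difference, but its failure to do so is not evidence of sameness. Sections 6 and 4.1 ask the tests to establish homogeneity and, in Section 6, agreement with published series. If the report then describes the sample as homogeneous, or as consistent with the literature, because the tests were not significant, that statement has no support.

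The second is a gap between intention and analysis. The plan itself expects pre-operative deficit to affect the signal, and it wants the signal related to histology. The analyses named for the aims do not use either variable. A reader of the results could learn how well the method discriminates in the cohort as a whole. That reader could not learn whether it does so differently in different kinds of tumour, or whether the eloquent contrast changes when the patient already has a deficit.

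**Working it through.** **1. The plan's own figure.** The only sample-size arithmetic is in Section 6.3: 50 patients × 6 datasets × 10 regions = 3,000 spectra, or 60 per patient. It reproduces at the lower end of the stated 10 to 20 regions per image. It is a count of readings. It gives no significance level, effect size or margin, so there is no plan figure to reproduce for the homogeneity tests.

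**2. What the homogeneity tests specify.** Section 4.1 lists the clinical variables to be collected. Neither 4.1 nor 6 names the groups to be compared, a significance level, an equivalence margin, a comparator series, or what follows if a test rejects. Section 4.3 admits intrinsic and extrinsic, primary and secondary disease of any histology. On diagnosis, then, the sample is heterogeneous before any test is run.

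**3. How little non-rejection would mean at this size (illustration).** Assume a two-sided 5% level and a true difference of *d* standard deviations between two groups of n₁ and n₂ patients. Power ≈ Φ(d·√(n₁n₂/(n₁+n₂)) − 1.96). For d = 0.5:

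| Split of 50 | √(n₁n₂/(n₁+n₂)) | Power | Missed |
|---|---|---|---|
| 25 / 25 | √12.5 = 3.54 | 42% | 58% |
| 35 / 15 | √10.5 = 3.24 | 37% | 63% |
| 40 / 10 | √8 = 2.83 | 29% | 71% |

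The level, effect size and splits are assumptions. The argument does not need them, because non-rejection would not prove homogeneity at any sample size.

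**4. Do the outcome comparisons depend on the tests?** No. Section 6.1 compares tumour with a neighbouring region, and 6.2 compares an eloquent area with its surroundings. Both are largely within patient, so patient-level confounding is limited. No exclusion, model or conclusion in Sections 6.1 to 6.3 is made conditional on the homogeneity tests.

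**5. Stated intention against named analysis.**

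| Variable | Intention | Analysis named |
|---|---|---|
| Histology / tumour group | 4.1: correlate signal with histological findings | 6.1: accuracy, sensitivity, specificity and ROC, with no result by group |
| Pre-operative deficit | 4.1 and 6.2: called crucial; a different signal is thought possible | 6.2: the tests of 6.1; none said to use deficit status |

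The correlations in Section 3.1 (with the operative view, MRI and neurophysiology) concern how the tissue is classified. They do not compare results between kinds of patient.

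**6. What descriptive results could deliver.** For a patient-level difference between two groups, the 95% half-width is about 1.96·√(1/n₁ + 1/n₂) between-patient SDs: 0.55 SD for 25/25, 0.60 for 35/15 and 0.69 for 40/10. For Aim 2 the number of patients is not given; 6.2 says only that "we will consider to perform multispectral/hyperspectral acquisition on patients undergoing surgery with neurophysiology monitoring", or awake surgery, will be considered. If 10 to 25 such patients are assumed, split about evenly by deficit, the half-width runs from 1.24 SD (5/5) to 0.78 SD (12/13).

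**The case against.** The strongest reply is that little hangs on the first point. The tests are a baseline description, nothing downstream uses them, and the comparisons are within patient. That stands, and it limits the consequence to the homogeneity statement itself. It does not rescue the wording, since two sections give proof of homogeneity as the purpose.

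A reader might infer that mixed histology confounds or invalidates the tumour-versus-brain result. The documents do not support this. Each tumour region is set against neighbouring tissue. Section 6.3 also says that image sets will be analysed separately because patients vary, and concedes that this variability cannot be fully accounted for. That text sits under Aim 3, so its reach to Aims 1 and 2 is uncertain, but it shows that heterogeneity was recognised.

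A reader might also infer that the plan ignores tumour type and deficit. It does not. Section 4.1 states a correlation with histological findings, though that may serve only as ground truth, and 4.1 and 6.2 state one with neurological status. The intention is present; the method is missing.

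Finally, this is a pilot, no section promises accuracy by tumour group, and small groups will give wide intervals. This is fair. It argues against powered subgroup tests and for labelling the results exploratory. It has less force for deficit status, because the plan itself calls that correlation crucial.

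**Conclusion.** The concern holds in two limited parts. First, the homogeneity tests in Sections 6 and 4.1 cannot do what they are said to do, and eligibility makes the target unrealistic. This is a matter of logic and rests on no assumed value; the 58% to 71% figures are illustration only. Its effect on the main comparisons is small.

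Second, the named analyses for Aims 1 and 2 would not show whether performance differs by tumour group or by pre-operative deficit, although the plan intends to relate the signal to both histology and neurological status. The size of any such difference cannot be derived from the documents. They give no expected accuracy, no within-patient correlation and no group sizes. It would therefore be wrong to conclude that an overall figure will conceal a particular difference, or to measure the gap by interval widths built on assumed accuracy.

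The change is worth making because it is cheap and most of it carries out what the plan already says it wants.

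**What to change.** 1. **Sections 6 and 4.1.** Replace the homogeneity tests with a descriptive case-mix table (diagnosis, intrinsic or extrinsic, primary or secondary, age, sex, neurological baseline) set beside the literature series. Give no p-values and make no claim of homogeneity.
2. **Section 6.2.** Carry out the stated correlation by reporting the eloquent versus non-eloquent contrast descriptively for patients with and without a recorded pre-operative deficit. Give the number of patients in each group.
3. **Section 6.1.** Beside any overall figure, report performance descriptively by broad tumour group, for example intrinsic and extrinsic, with histology counts because each group remains mixed. Label it exploratory. Use intervals that respect the clustering of readings within patient, such as a patient-level bootstrap, or list per-patient results where a group is small.

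**Cost.** SAP wording and two or three tables; no new patients. Section 4.1 already collects the clinical variables. Section 8.3's list of clinical data held on College Computers omits clinical status, age and sex, so it must be aligned with 4.1 or the tables made on the NHS side. The downside is wide intervals and possibly very small Aim 2 groups.

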## 6.1. FIRST AIM

*Detect structural differences between brain tumour tissue and surrounding brain.*

The Regions Of Interest (ROI) for multispectral/hyperspectral acquisition will be delineated on both peri-operative images (MRI scan) and intra-operative images as extrapolated from the intra-operative videos. We will focus our analysis on three main regions:

- normal brain tissue - brain tissue not infiltrated by tumour or edema, nor grossly pathological on pre-operative images or intra-operative images;
- suspected infiltrated brain tissue – tissue surrounding the tumour where there is strong radiological and clinical suspicion of infiltrative disease or edema;
- tumour tissue – margins and core of the tumour on pre-operative images and intra-operative findings.

The signal in one region of the tumour will be compared to a neighbouring 'healthy' region. The signal itself will come from a processed set of images of the brain, where we will fit the data using one of our established models to extract an indication of tissue oxygenation (as a %) on a per-pixel basis.

The comparison between the set of readings obtained from normal brain will be performed using Principal Component Analysis (PCA) and Linear Discriminant Analysis (LDA) or more advanced techniques including, for example, machine learning. Statistics will be collected on accuracy, sensitivity, specificity, ROC analysis.

We will also need to take pictures and/or videos of the surgical field in order to correlate the expected anatomical location of the tumour and infiltrated areas with the intra-operative finding. The surgical field is limited to the area under the microscope or endoscope

magnification, therefore no identifiable pictures or videos will be taken at any point during the study.

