Surgery will be conducted following standard procedures, already validated in clinical practice. The surgeons performing the procedures will be [name] [name] (CI), [name] (PhD student and clinical fellow), [name] (Consultant Neurosurgeon), and [name] (Neurosurgery Trainee and Clinical Lecturer). Surgeons will work in teams, each team with no more than two surgeons. [name] and one of his collaborators will be present in theatre to facilitate images acquisition. For each researcher not normally involved in clinical practice, research passport will be provided. Intra-operative imaging data and spectra will be collected during tumour resection, but the analysis on the spectra will be performed on a different time and setting, in order not to excessively prolong the surgical procedure.

Researchers will collect spectral data up until the statistical model used for multivariate analysis does not longer improve the degree of accuracy (see Section 6 - statistical analysis).

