### 6.3. THIRD AIM

*Test whether the combination of multispectral/hyperspectral analysis and fluorescence could provide useful new insight into the detection of different perfusion patterns of brain tumours VS normal brain tissue*

Multispectral/hyperspectral imaging will be tested to check whether it can increase the distinction of the fluorophore signal compared with the background. Dedicated statistical software will be used for this analysis.

Each image set will be analysed separately because there will be variability between patients and we will not be able to fully account for this with the limited number of datasets that we are going to record (a well-known problem with many biophotonics/optical techniques). This will all be done offline after the surgery is complete, with a primary aim is to observe whether the technique is capable of detecting changes in the tissue.

We will collect spectral data up until the statistical model used for multivariate analysis does not longer improve the degree of accuracy. We will aim to recruit approximately 50 patients with diagnosis of neuro-oncological disease. Each patient will have an average acquisition of 6 datasets. As each dataset will correspond to an image, this will be divided into many reading regions (from 10 to 20) for a total of approximatively 60 measurements per patient. Based on this estimation, we approximate that 50 patients will provide a spectral database of 3.000 spectra, which we calculate is adequate for diagnostic validation purposes [14].

Same tests as section 6.1 will be run to statistically validate the data.

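### Data collection is steered by overall accuracy, which shifts with an unstated class mix and can stay flat while discrimination improves, and no headline performance measure is named

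*Combined protocol and SAP*

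**What the plan says.** For the first aim (tumour against surrounding brain), section 6.1 plans PCA with LDA, or more advanced techniques such as machine learning. It then states: "Statistics will be collected on accuracy, sensitivity, specificity, ROC analysis". The four measures stand side by side and none is called primary. Section 6.2 carries them to eloquent against non-eloquent tissue: "Same tests as section 6.1 will be run to statistically validate the data". Section 6.3 does the same for the third aim.

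One of the four has a second job. Section 4.1 says: "Researchers will collect spectral data up until the statistical model used for multivariate analysis does not longer improve the degree of accuracy". Sections 6.3 and 10 repeat the rule. Nowhere is accuracy defined further, for instance as raw or balanced, or as per region or per patient.

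On class mix, section 6.3 expects about 6 images per patient, each split into 10 to 20 reading regions, and gives no breakdown by tissue class. In section 6.2 the contrast is described thus: "we will focus our analysis on the comparison between a supposed eloquent area and its surrounding brain tissue". No number of regions per class, class weighting, LDA prior or minimum sensitivity is stated.

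**The concern.** Overall accuracy is an average of sensitivity and specificity weighted by the class shares in the sample. Here those shares come from how the field is framed and how regions are drawn, not from the disease. Two consequences follow.

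First, accuracy is not comparable between aims, images or patients when the mix differs, and with no headline measure named, the choice among four figures stays open until the results are known.

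Second, when one class is small and the signal modest, accuracy sits close to the majority share and hardly responds to better discrimination. A rule that ends collection when accuracy stops improving could then fire while the model is still getting better. It could also be moved by a change in class mix among later patients, with no change in the signal.

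**Working it through.** **The plan's own figure.** Section 6.3 gives about 50 patients, 6 images each and 10 to 20 regions per image. At 10 regions, 6 × 10 = 60 measurements per patient and 50 × 60 = 3,000 spectra, which matches the stated total. At 15 regions the total would be 4,500, and at 20 it would be 6,000. None of these is split by class, so the class share below is an assumption and is shown over a range.

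**Dependence on class mix, with no model.** Let p be the eloquent share.

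- Accuracy = p × sensitivity + (1 − p) × specificity.
- Balanced accuracy = (sensitivity + specificity) / 2.

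Take an assumed classifier with sensitivity 10% and specificity 95%. At p = 10%, accuracy is 0.10 × 0.10 + 0.90 × 0.95 = 86.5%. At 20%, 30% and 50% it is 78.0%, 69.5% and 52.5%. Balanced accuracy is 52.5% throughout.

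**Illustration with LDA.** Assumptions, none from the documents: two normal classes with equal variance, separation d in SD units, and LDA with sample-proportion priors.

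- Cut-off t = d/2 + ln((1 − p)/p)/d.
- Sensitivity = 1 − Φ(t − d); specificity = Φ(t).
- AUC = Φ(d/√2), which does not depend on p.

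Worked case, d = 1 and p = 2/15 (13.3%): t = 0.5 + ln(6.5) = 2.372. Sensitivity = 1 − Φ(1.372) = 8.5% and specificity = Φ(2.372) = 99.1%. Accuracy = 87.0%, against 13/15 = 86.7% for always answering non-eloquent.

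Range at d = 1, with AUC = Φ(0.707) = 0.76 in every row:

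| Eloquent share | Accuracy | Sensitivity |
|---|---|---|
| 10% | 90.1% | 4.5% |
| 13.3% | 87.0% | 8.5% |
| 20% | 81.4% | 18.8% |
| 30% | 74.7% | 36.4% |
| 50% | 69.1% | 69.1% |

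**Response to a real gain.** Keep p = 2/15 and use the separation as a stand-in for how well the model discriminates. At d = 0.5, t = 0.25 + 1.872/0.5 = 3.994, so almost nothing is called eloquent and accuracy equals the majority share, 86.7%; AUC = Φ(0.354) = 0.64. At d = 1, accuracy is 87.0% and AUC 0.76. Discrimination rises by 0.12 on the AUC scale while accuracy gains 0.3 percentage points.

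**The case against.** The strongest reply is that the report is already protected. Sensitivity, specificity and ROC analysis are planned for all three aims. In the worked case a reader would see 8.5% sensitivity beside 87.0% accuracy, and the ROC curve would show the AUC of 0.76. An uninformative signal would give an AUC of 0.5. This stands, and it rules out the tempting inference that a classifier missing nearly all eloquent tissue could pass as a success on accuracy alone. Nor do the documents make accuracy the lead statistic: it is listed first, but nothing ranks it.

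The illustration also rests on choices that the plan does not make. It states no priors and allows methods other than LDA. With equal priors at d = 1, sensitivity and specificity are both 69%. Imbalance is likely in section 6.2 but not built in: the investigators delineate the regions and could equalise them, and section 6.1 sets a tumour region against a neighbouring healthy one, which is closer to paired sampling. The flat response needs both a small class and a weak signal. At d = 2 and a 2/15 share, sensitivity is 53% and accuracy 91%, clearly above the majority share.

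Finally, this is an offline pilot that does not affect care. That limits the seriousness of the point.

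What remains is the collection rule. There accuracy stands alone, and the other three measures offer no protection.

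**Conclusion.** The point holds for the collection rule and for the unranked choice of measure. Under the stated assumptions, a signal of fixed quality (AUC 0.76) yields accuracy anywhere from 69.1% to 90.1% as the eloquent share goes from 50% to 10%. At a 13.3% share, a rise in AUC from 0.64 to 0.76 moves accuracy by 0.3 percentage points, which a rule based on accuracy could read as no improvement. The size depends on the assumed share, separation and priors, and the problem disappears with equal shares. The documents do not show that imbalance will occur, or that missed eloquent tissue would go unreported. This is a cheap improvement, not a flaw that invalidates the study.

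**What to change.** In sections 4.1, 6.3 and 10, replace accuracy with AUC as the quantity whose improvement governs data collection. If all three tissue classes of section 6.1 are classified together, state whether the AUC is pairwise or averaged, since a single AUC is otherwise undefined.

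In section 6.1, and so in 6.2 and 6.3, name AUC as the headline measure and report balanced accuracy beside it. AUC should come first because balanced accuracy is read at one cut-off and so still reflects the priors used. Wherever raw accuracy is quoted, print the majority-class share next to it.

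There is no need to prescribe equal LDA priors: for two classes they only move the cut-off and leave the ROC curve unchanged.

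The cost is a few lines of wording. No extra patients or measurements are needed, and the measures come from statistics already planned. The one drawback is that the headline figure may look less favourable than raw accuracy.
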